## 5. PROCEDURES

### 5.1. Screening Evaluations

This study will be conducted at the University of Washington, Seattle, USA; other centers may be considered to join. Each subject who enters into the screening period for the study receives a unique subject identification number before any study-related procedures are performed. The subject identification number will be assigned. This number will be used to identify the subject throughout the clinical study and must be used on all study documentation related to that subject.

The subject identification number must remain constant throughout the entire clinical study; it must not be changed after initial assignment, including if a subject is rescreened.

Before subjects may be entered into the study, the Sponsor-Investigator requires a copy of the written IRB/IEC approval of the protocol, informed consent form, and all other subject information and/or recruitment material, if applicable. A signed and dated Institutional Review Board (IRB) approved informed consent form (latest approved version) must be obtained from each subject prior to performing any study-specific procedures. All subjects must personally sign and date the consent form before commencement of study-specific procedures.

Screening evaluations will be performed for all subjects to determine study eligibility. These evaluations must be obtained  $\leq 28$  days prior to enrollment. Baseline imaging should be obtained as close to initiation of protocol therapy as possible. Any questions regarding subject eligibility should be directed to the Sponsor-Investigator for approval.

The following procedures are to be completed during the screening period, after signed informed consent has been obtained, designated in the Schedule of Assessments found in Table 4 and Table 5.

- Demographics (if allowed by local regulations, date of birth, sex, race, and ethnicity)
- Physical examination (including medical/cancer history, ECOG performance status assessment, weight)
- Prior/concomitant medications and procedures evaluation to include all medications taken  $\leq 28$  days prior to date of informed consent
- Vital signs (temperature, sys/dias blood pressure, respiration rate, and pulse)
- ECG
- Left ventricular ejection fraction (LVEF, by echocardiogram or MUGA)
- Local Laboratory Assessments: chemistry, complete blood count (CBC with differential, platelet count, urinalysis, pregnancy test (women of child-bearing potential, includes tubal ligations), thyroid panel (TSH, T3, T4), HIV, hepatitis B surface antigen, hepatitis B core antibody (HBV cAb), hepatitis C antibody, lipids
- CT or MRI, must be done within 28 days of C1D1, but preferably should be done as close to the day of enrollment as possible

- Optional: Subjects who consent for pre-treatment tissue collection for biomarker analysis shall provide either fresh-frozen or formalin-fixed paraffin-embedded (FFPE) tumor blocks or unstained slides (min 10). Fresh tissue collection may only be obtained if clinically feasible and without undue risk to the subject.

A subject is considered enrolled when the investigator decides that the subject has met all eligibility criteria and an enrollment packet has been completed. The investigator is to document this decision and date, in the subject's medical record and in/on the electronic case report form (eCRF).

## **5.2. Treatment Period**

A subject is considered enrolled on study day 1 when the IP, nab-Sirolimus, is first administered. Nab-Sirolimus is to be administered after all other protocol-specified pre-dose assessments have been performed during each visit that it is required. Subjects will continue therapy until disease progression, unacceptable AEs, or withdrawal of consent.

### **5.2.1. Day 1 Assessment**

The following assessments will be performed on Day 1 of each cycle, unless otherwise specified:

- Physical examination
- Weight assessment
- Height assessment (only in C1)
- Concomitant medication and procedures evaluation
- Vital signs (temperature, sys/dias blood pressure, respiration rate, and pulse)
- ECOG performance status
- CBC with differential
- Clinical chemistry panel
- ECG and lipid panel (every even visit, i.e. C2, C4, etc.)
- Urinalysis
- Adverse Event assessment
- Rapamycin levels (only in Phase 1, C1 and C2)
- 60-minute observation window post end of infusion for Cycle 1. If a subject completes Cycle 1 with no infusion related reactions, the observation period may be omitted for Cycle 2 and onwards. If at any time the subject experiences an infusion related reaction, the 60-minute post-dose observation period will be reinstated.

All Day 1 evaluations for Cycle 1 may be omitted if screening evaluations are performed within 72 hours of Cycle 1 Day 1. All Day 1 laboratory assessments and physical examination for Cycle 2+ may be performed up to 72 hours prior to planned treatment.

### **5.2.2. Day 8 Assessment**

The following assessments will be performed on Day 8 of each cycle, unless otherwise specified:

- Physical examination
- Weight assessment
- Vital signs (temperature, sys/dias blood pressure, respiration rate, and pulse)
- Concomitant medication and procedures evaluation
- CBC with differential
- Clinical chemistry panel
- Adverse Event assessment
- Rapamycin levels (only in Phase 1, C1 and C2)

For subjects receiving treatment on Day 8, all Day 8 laboratory assessments and physical examination may be performed up to 72 hours prior to planned treatment.

### **5.2.3. Day 15 Assessment**

The following assessments will be performed on Day 15 of Cycle 1 and 2 only.

- Physical examination
- Weight assessment
- Vital signs (temperature, sys/dias blood pressure, respiration rate, and pulse)
- Concomitant medication and procedures evaluation
- CBC with differential
- Clinical chemistry panel
- Adverse Event assessment
- Rapamycin levels (only Phase 1)

**Table 6. Analyte Listing**

Chemistry	Hematology	Urinalysis	Other Labs
Sodium	WBC	Specific gravity	Pregnancy test
Potassium	RBC	pH	HIV
Bicarbonate	Hemoglobin	Blood	HBV sAg
Chloride	Hematocrit	Protein	HBV cAb
Total protein	MCV	Glucose	HCV Ab
Albumin	MCH	Ketones	Total Cholesterol
Calcium	MCHC	Microscopic	HDL
Magnesium	RDW		LDL
Phosphorus	Platelets		Triglyceride
Glucose	Differential:		TSH, T3, T4
BUN	-Neutrophils		Rapamycin
Creatinine	-Lymphocytes		
Total bilirubin	-Monocytes		
Alkaline phosphatase	-Eosinophils		
AST (SGOT)	-Basophils		
ALT (SGPT)			
Amylase			
Lipase			

#### **5.2.4. Response Assessment**

Tumor response will be assessed by CT or MRI scan of the chest, abdomen, and pelvis (CAP) per institutional guidelines; image preparation and evaluation will follow the specifications provided in the RECIST version 1.1. The same modality (CT or MRI) must be used at screening and throughout the study.

CT/MRI scans to be performed at the following frequency:

- ≤4 weeks prior to C1D1 (as close to C1D1 as possible) (screening)
- Followed by every 6 weeks from C1D1 ( $\pm$  1 week) for the first year; then every 12 weeks ( $\pm$  1 week) until disease progression or unacceptable toxicity. End of Treatment Visit CT/MRI should be performed only for those subjects that discontinue treatment for a reason other than disease progression.

An unscheduled scan for suspected disease progression may be performed at any time. However, adherence to the planned imaging schedule is critical regardless of dose delays or unscheduled or missed assessments. Determination of disease progression for clinical management of subjects on study will be assessed at the local site. If an initial observation of objective response (CR or PR) is made, a confirmation scan should be done at 6 weeks after initial observation.

#### **5.3. End of Treatment Visit Assessment**

The EOT Visit is a safety follow-up visit that is to be performed after the last dose of nab-Sirolimus or pazopanib, whichever is later ( $\pm$ 3 days). All efforts should be made to conduct this visit. If it is

not possible to conduct the EOT Visit, documentation of efforts to complete the visit should be provided.

The following procedures will be completed at the EOT Visit as designated in the Schedule of Assessments in Table 4 and Table 5.

- Physical examination (including ECOG Performance Status assessment, weight)
- Vital signs (e.g., blood pressure, pulse, respiration rate, temperature)
- Concomitant medication and procedures evaluation
- Adverse Event assessment
- Laboratory assessments: chemistry, CBC with differential, platelet count, pregnancy test (women of child-bearing potential, includes tubal ligations), urinalysis
- Imaging Assessment: CT/MRI is to be performed at the end of study visit only for those subjects that discontinue treatment for a reason other than disease progression per RECIST v1.1

#### **5.4. 30-Day Follow Up Visit**

Active subject participation is complete after the 30-Day Follow-Up Visit. The 30-Day Follow-Up Visit is a safety follow-up visit that is to be performed 30 days after the last dose of protocol therapy ( $\pm 7$  days). All efforts should be made to conduct this visit. If it is not possible to conduct the 30-Day Follow-Up Visit, documentation of efforts to complete the visit should be provided.

The following procedures will be completed at the 30-Day Follow-Up Visit as designated in the Schedule of Assessments in Table 4 and Table 5.

- Physical examination (including ECOG Performance Status assessment, weight)
- Vital signs (e.g., blood pressure, pulse, respiration rate, temperature)
- Concomitant medication and procedures evaluation
- Adverse Event assessment
- Laboratory assessments: chemistry, CBC with differential, platelet count, pregnancy test (women of child-bearing potential, includes tubal ligations)
- Left ventricular ejection fraction (LVEF, by echocardiogram or MUGA)

#### **5.5. Rapamycin Trough levels**

Assays for rapamycin will be performed on subjects in the dose-finding (phase 1) portion of the study, who received nab-Sirolimus during C1 and C2, to determine trough levels, assessed via local lab. The rapamycin sampling schedule is outlined below, based on dosing schedule.

- **Q2/3W Dosing:**
  - Cycle 1:

- C1D8: Prior to treatment (within 15 minutes pre-infusion)
- C1D15: Day 15 collection any time
- Cycle 2:
  - C2D1: prior to treatment (within 15 minutes pre-infusion)
  - C2D8: prior to treatment (within 15 minutes pre-infusion)
  - C2D15: Day 15 collection any time
- **Q1/3W Dosing:**
  - Cycle 1:
    - C1D1: End of infusion (within +10 minutes of EOI) and Optional 24-hour post dose (Day 2, +/- 2 hours),
    - C1D8: Day 8 collection any time
    - C1D15: Day 15 collection any time
  - Cycle 2:
    - C2D1: prior to treatment (within 15 minutes pre-infusion)
    - C2D8: Day 8 collection any time
    - C2D15: Day 15 collection any time

## **5.6. Follow-up Period for Survival and Initiation of Anticancer Therapy**

Post-treatment survival time and any subsequent anticancer therapy information status will be monitored approximately every 12 weeks ( $\pm 3$  weeks) from 30-Day Follow Up Visit or more frequently as needed, until death, withdrawal of consent, or the study closes, whichever is earliest. This evaluation may be by record review and/or telephone contact.

## 6. DESCRIPTION OF STUDY TREATMENTS

### 6.1. Nab-Sirolimus

#### 6.1.1. Nab-Sirolimus/Pazopanib Dosage, Administration, and Schedule

Treatment with nab-Sirolimus combined with pazopanib will continue until disease progression, unacceptable toxicity, or withdrawal of consent. A physician must be available at the time of administration of IP on dosing days that correspond to study visits. Supportive care per the institution's normal standard of care including concomitant medications can be provided at the investigator's discretion.

**Table 7 - Day 1 and Day 8 Dosing Levels (Closed – Enrolled under Am2, v3.0 or earlier)**

Dose Levels (Day 1 and Day 8 Dosing)	Planned Starting Dose of nab-Sirolimus in mg/m 	Planned Starting Dose of Pazopanib in mg
-2	30	800
-1	45	800
0	60	800
1	75	800
2	100	800
0B	60	400
1B	75	400
2B	100	400
-1B	45	400
-2B	30	400

**Table 8 - Day 1 Only Dosing Levels**

Dose Levels (Day 1 Only Dosing)	Planned Starting Dose of nab-Sirolimus in mg/m 	Planned Starting Dose of Pazopanib in mg
-2C	15	400
-1C	20	400
0C	30	400
1C	45	400
2C	60	400
3C	75	400
4C	100	400

### **6.1.2. Nab-Sirolimus Dose Modification and Stopping Rules**

If treatment cannot be administered on the planned visit date, nab-Sirolimus may be administered  $\pm 3$  days from the scheduled date. Prior to nab-Sirolimus administration, subjects must meet the following hematological requirements for dosing on every dosing day:

- ANC  $\geq 1.5 \times 10^9/L$
- Platelet count  $\geq 100 \times 10^9/L$
- Hemoglobin  $\geq 9.0 \text{ g/dL}$

The treatment may be held (delayed) up to 21 days due to toxicity. Treatment may also be interrupted for situations other than treatment-related AEs such as medical/surgical events or logistical reasons not related to study therapy. Participants should be placed back on study therapy within 21 days of the scheduled interruption, unless otherwise discussed with the Sponsor-Investigator. The reason for interruption should be documented in the subject's study record.

If the dose held or missed was to be Day 1 of the next cycle, the next cycle will not be considered to start until the day the first dose is actually administered to the subject.

If the subject is dosing on a q2/3w schedule, if the dose held or missed was to be Day 8, that week becomes the week of rest. Next dose becomes Day 1 of a new cycle. The cycle with the missed Day 8 dose would become 14 days long versus the normal 21-day cycle. If the cycle with the missed Day 8 dose is Cycle 1 or Cycle 2, the Day 15 visit would also be omitted. If the subject is dosing on a q1/3w schedule, a cycle is not considered to have begun until the subject receives the Day 1 dose. If the subject misses a Day 8 or Day 15 visit, the cycle continues without interruption and the visits are recorded as missed. The following cycle is considered to have begun when the subject receives their next dose.

In the event of clinically significant AE in any part of the study, treatment may be held, and supportive therapy administered as clinically indicated. If the toxicity or event is not grade 3/4 and resolves to baseline or grade 1 in less than or equal to 21 days of stopping therapy, then treatment may be restarted.

Dose reduction of nab-Sirolimus to the next lower dose level should be considered as clinically indicated for subjects who are receiving nab-Sirolimus at above the lowest dose level. In phase 1, once a dose has been reduced, it may not be increased to the previous level. In phase 2, if an AE resolves to grade 1 or baseline at the reduced dose level, and no additional toxicities are seen during the following cycle of study treatment at the reduced dose, the dose may be re-escalated to the previous dose level.

The maximum delay between a missed scheduled dose and the next one (whichever dose was missed) should not be longer than 21 days. If a dose delay over 21 days is required, Sponsor-Investigator Approval is required, otherwise the subject should be discontinued. If Sponsor-Investigator approval is granted, a secondary approval is required to restart study treatment after  $\geq 21$  days of interruption. If the toxicity does not resolve to at least grade 1 in less than 21 days, withdrawal from the treatment with the IP is recommended. However, if the investigator and

Sponsor-Investigator agree that further treatment would benefit the subject, treatment can continue with at least 1 dose level dose reduction. Adjustments to the dosing schedule may be made, at investigator discretion, according to Section 6.3.

**Table 9. Dose Modification Algorithms for Adverse Events Possibly Related to ABI-009 (See also Table 10 and Table 11)**

System/Organ	Adverse Event	CTCAE Grade v5.0	Dose modification Algorithm
Mucosa a	Stomatitis, mucosal inflammation	Grade 2 or 3	Hold ABI-009 until resolution to grade 1 or baseline and restart at the same dose for 1 st occurrence; for subsequent occurrences, drug will be restarted at a reduced dose; provide supportive care as clinically indicated.
		Grade 4	Permanently discontinue ABI-009.
Skin and Subcutaneous Tissue Disorders	Skin rash	Grade 2	Tolerable: Continue ABI 009 at full dose, monitor as clinically indicated.
			Intolerable: Hold ABI-009 until resolution to grade 1 or baseline and restart at the same dose for 1 st occurrence; for subsequent occurrences, drug will be restarted at a reduced dose; provide supportive care as clinically indicated.
		Grade $\geq 3$	Hold ABI-009 until resolution to grade 1 or baseline; for subsequent events, drug will be restarted at a reduced dose; provide supportive care as clinically indicated.
Gastrointestinal Disorders	Diarrhea despite optimal medication	Grade 2	Hold ABI-009 until resolution to grade 1 or baseline and restart at the same dose for 1 st occurrences; for 2 nd and subsequent events, drug will be restarted at a reduced dose; provide supportive care as clinically indicated.
		Grade $\geq 3$	Hold ABI-009 until resolution to grade 1 or baseline; for subsequent events, drug will be restarted at a reduced dose; provide supportive care as clinically indicated.
Metabolic disorders	Hyperlipemia (cholesterol, triglycerides)	Grade 3	If this is persistent for 2 months, reduce by 1 dose level at start of next cycle.
		Grade 4	If this is persistent for 1 month, reduce by 1 dose level at start of next cycle.
	Hyperglycemia		

		Grade $\geq 3$	Hold ABI-009 until grade 2 or less, restart 1 dose level lower.
Hypokalemia		Grade 2	Withhold treatment until Grade $\leq 1$ , restart at the same dose level. If recurs, restart 1 dose level lower.
		Grade $\geq 3$	Withhold treatment until Grade $\leq 1$ , restart at 1 dose level lower. If recurs, permanently discontinue ABI-009.
Respiratory events	Pneumonitis, bronchiolitis obliterans, and/or organizing pneumonia, Interstitial Lung Disease	Grade 2	Hold ABI-009 immediately for up to 3 weeks until resolved to $\leq$ grade 1, then reduce by 1 dose level. If it is still a Grade 2 after 3 weeks, discontinue treatment. If grade 2 recurs after resuming ABI-009 at a reduced dose level, discontinue treatment.  For noninfectious pneumonitis, if cough is troublesome, prescribe corticosteroids.
		Grade $\geq 3$	Permanently discontinue ABI-009.  For grade 3 noninfectious pneumonitis, prescribe corticosteroids if infection is ruled out. Hold ABI-009 until recovery to $\leq$ grade 1; may restart within 3 weeks at reduced dose level if evidence of clinical benefit. Subjects will be withdrawn from the study if they fail to recover to $\leq$ grade 1 within 3 weeks.  For grade 4 noninfectious pneumonitis, discontinue ABI-009.
Infections and infestations	Infections	Grade 3	Withhold treatment until resolved, then restart at 1 dose level lower. If recurs, permanently discontinue ABI-009.
		Grade 4	Withhold treatment until resolved. Restart at 1 dose level lower,. If recurs, or permanently discontinue ABI-009.
General Disorders	Hemorrhage	Grade 2 or 3	Withhold treatment until Grade $\leq 1$ , then resume at 1 dose level lower. If recurs, permanently discontinue ABI-009.

		Grade 4	Permanently discontinue ABI-009.
Other Adverse Reactions	Other Adverse Reactions	Grade 3	Withhold treatment until Grade $\leq 1$ , then restart at the same dose level. If recurs, restart at 1 dose level lower.
		Grade 4	Permanently discontinue ABI-009.

a Subjects who develop or are at risk for stomatitis, a steroid mouthwash (10 mL dexamethasone 0.1 mg/mL oral solution four times daily) could be considered.

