Oral rapamycin and currently available rapalogs induce common side effects including hypertension, maculopapular rash (75%), mucositis (50%), asthenia (40%), nausea (43%), thrombocytopenia, metabolic abnormalities and more rarely pneumonitis (8%, 3% grade 3) sometimes fatal. The most frequently occurring grade 3 or 4 AEs were hyperglycemia (17%), hypophosphatemia (13%), anemia (9%), and hypertriglyceridemia (6%). These side effects lead to the discontinuation of the treatment in 60% of subjects in some studies.

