#### **6.1.3.2. Criteria for Conditional Withholding of nab-Sirolimus Due to Potential Hepatotoxicity**

For subjects who do not meet the criteria for permanent discontinuation of ABI-009 and have no underlying liver disease, and eligibility criteria requiring normal transaminases and TBL at baseline or subjects with underlying liver disease and baseline abnormal transaminases, the following rules are recommended for withholding of nab-Sirolimus:

- Elevation of either AST or ALT according to the following schedule:

AST or ALT elevation
>8 x ULN at any time
>5 x ULN but <8 x ULN for ≥2 weeks
>5 x ULN but <8 x ULN and unable to adhere to enhanced monitoring schedule
≥3 x ULN with clinical signs or symptoms that are consistent with hepatitis (such as right upper quadrant pain/tenderness, fever, nausea, vomiting, jaundice).

- OR: Total bilirubin >3 x ULN at any time
- OR: Alk Phos >8 x ULN at any time

Nab-Sirolimus should be withheld pending investigation into alternative causes of DILI. Re-challenge may be considered if an alternative cause for impaired liver tests (ALT, AST, and ALP) and/or elevated TBL is discovered and the laboratory abnormalities resolve to normal or baseline.

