## 6.5. Dose Modification Algorithms for Adverse Events Possibly Related to nab-Sirolimus and Pazopanib

**Table 11 - Dose Modification Algorithms for Overlapping Adverse Events Possibly Related to nab-Sirolimus and Pazopanib (See also Table 9 and Table 10)**

System/Organ	Adverse Event	CTCAE Grade v5.0	Dose Modification Algorithm
Hematologic toxicity	Thrombocytopenia, Anemia	Grade 2	
Nab-Sirolimus: Nab-Sirolimus can be administered if meeting the following hematological requirements: platelets <math>>100 \times 10^9/L</math> and hemoglobin <math>\geq 8</math> g/dL.
 
Pazopanib: No changes to pazopanib dosing.

		Grade 3-4	
nab-Sirolimus: Hold nab-Sirolimus immediately for the remainder of that cycle. Repeat blood collection within 3 days. Nab-Sirolimus can resume once meeting following requirements: platelet count <math>>100 \times 10^9/L</math> and hemoglobin <math>\geq 8</math> g/dL. For 2nd and subsequent events, drug will be restarted at a reduced dose; G-CSF may be given as deemed indicated.
 
Pazopanib: Delay pazopanib until platelets <math>\leq</math> grade 1, resume pazopanib with one dose level reduction.

	Neutropenia, Febrile or Afebrile	Grade 3	
nab-Sirolimus: Hold nab-Sirolimus. Repeat blood collection within 3 days. Nab-Sirolimus can resume once meeting following requirements: absolute ANC <math>\geq 1.5 \times 10^9/L</math>. For 2nd and subsequent events, drug will be restarted at a reduced dose; G-CSF may be given as deemed indicated.
 
Pazopanib: Delay pazopanib until <math>\leq</math> grade 2, and then resume pazopanib at the current dose level.

		Grade 4	
Nab-Sirolimus: Hold nab-Sirolimus. Repeat blood collection within 3 days. Nab-Sirolimus can resume once meeting following requirements: absolute ANC <math>\geq 1.5 \times 10^9/L</math>. For 2nd and subsequent events, drug will be restarted at a reduced dose; G-CSF may be given as deemed indicated.
 
Pazopanib: Delay pazopanib until <math>\leq</math> grade 2, then resume pazopanib with one dose level reduction.

Hepatic Toxicity	Hepatic Failure	Grade 3	
Nab-Sirolimus: See Section 6.1.3.1 and 6.1.3.2.
 
Subjects with ALT/AST > 3 x ULN, or Total Bilirubin > 3 x ULN, or Alk Phos > 8 x ULN are recommended for withholding of nab-Sirolimus.
 
Pazopanib: Discontinue pazopanib.

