	ALT, AST, or Bilirubin Elevation	Grade 2	
Nab-Sirolimus: See Section 6.1.3.1 and 6.1.3.2.
 
Subjects with ALT/AST > 3 x ULN, or Total Bilirubin > 3 x ULN, or Alk Phos > 8 x ULN are recommended for withholding of nab-Sirolimus.
 
Pazopanib: Continue pazopanib, but monitor weekly until ALT, AST, and bilirubin return to ≤ grade 1.

		Grade 3-4	
Nab-Sirolimus: See Section 6.1.3.1 and 6.1.3.2.
 
Subjects with ALT/AST > 3 x ULN, or Total Bilirubin > 3 x ULN, or Alk Phos > 8 x ULN are recommended for withholding of nab-Sirolimus.
 
Pazopanib: Delay pazopanib until improved to ≤ grade 1. Restart treatment with one dose level reduction of pazopanib.

	ALT/AST and Bilirubin (Grade 2 or greater ALT/AST elevation with concurrent Grade 2 or greater bilirubin elevation)	Grade 2+	
Nab-Sirolimus: Discontinue nab-Sirolimus.
 
Pazopanib: Discontinue pazopanib.

Other Adverse Reactions	Other Adverse Reactions	Grade 3	Withhold treatment until Grade ≤ 1, then restart at the same dose level. If recurs, restart at 1 dose level lower.

		Grade 4	Permanently discontinue nab-Sirolimus.
--	--	---------	----------------------------------------

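### Two nab-Sirolimus safety rules conflict as written: restart after Grade 3 noninfectious pneumonitis (Table 9), and the ALT/AST level for withholding (Table 11 against Section 6.1.3.2)

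*Combined protocol and SAP*

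**What the plan says.** **Respiratory events (Section 6.1.2, Table 9).** One row covers pneumonitis, bronchiolitis obliterans, organizing pneumonia and interstitial lung disease. For Grade 3 or higher, the cell begins "Permanently discontinue ABI-009" and names no exception. It continues: "For grade 3 noninfectious pneumonitis, prescribe corticosteroids if infection is ruled out". The drug is then held until recovery to Grade 1 or better, and the subject "may restart within 3 weeks at reduced dose level if evidence of clinical benefit". Subjects who do not recover within 3 weeks are withdrawn. A last line discontinues the drug for Grade 4 noninfectious pneumonitis.

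**Liver (Section 6.5, Table 11).** Three cells carry the same nab-Sirolimus text: Hepatic Failure Grade 3, and single ALT, AST or bilirubin elevation at Grade 2 and at Grade 3-4. Each begins "See Section 6.1.3.1 and 6.1.3.2". Each then states that subjects with ALT/AST above 3 x ULN, bilirubin above 3 x ULN or alkaline phosphatase above 8 x ULN "are recommended for withholding of nab-Sirolimus". No symptom or duration condition is attached.

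**Liver (Section 6.1.3.2).** Withholding is recommended for ALT/AST above 8 x ULN at any time, or between 5 and 8 x ULN if this lasts at least 2 weeks or the subject cannot follow enhanced monitoring. A further criterion is "≥3 x ULN with clinical signs or symptoms that are consistent with hepatitis". The section describes its population partly by "eligibility criteria requiring normal transaminases and TBL at baseline", and otherwise as subjects with liver disease and abnormal baseline transaminases. Inclusion criterion 5b admits AST and ALT up to 2.5 x ULN.

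**The concern.** In each place an investigator with one patient and one set of results can find two stated actions and no rule for choosing between them.

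For pneumonitis, the first sentence of the cell ends the drug for good and a later sentence allows it back at a lower dose. The protocol's own background on oral rapamycin and rapalogs (Section 1.2.1) lists "more rarely pneumonitis (8%, 3% grade 3) sometimes fatal", so a permanent-stop rule for this event should not have to be interpreted.

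For the liver, an investigator who reads Table 11 would withhold at 4 x ULN. One who follows its cross-reference to 6.1.3.2 may find that no criterion is met, and dose. The rule is likely to be used: Table 3 already records one ALT increase as a dose-limiting toxicity in the first three cohorts, which started pazopanib at 800 mg. Section 5.1 says that other centers may join, which makes divergent readings more likely.

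**Working it through.** The plan gives no figure to reproduce here. The check sets the rules side by side.

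**1. Table 9, Grade 3 or higher respiratory cell.** Take a subject with Grade 3 noninfectious pneumonitis who recovers to Grade 1 at 2 weeks and shows clinical benefit.

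- Opening sentence: permanent stop, no restart.
- Later paragraph: restart allowed at a reduced dose, since 2 weeks is within the 3-week limit.

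There are two ways to read the cell:

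- If the opening sentence governs everything, the restart provision has no effect and the Grade 4 line is redundant.
- If the later paragraphs are an exception, the opening sentence still governs the other events in the row, and the Grade 4 line marks where the exception ends.

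The second reading makes better sense of the cell. But pneumonitis is the first event named in the row, and no word marks the exception.

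**2. ALT/AST withholding.** Assumptions: the event is graded 2 or higher (the documents give no CTCAE cut-offs) and is possibly related. Bilirubin is at most 2 x ULN and below Grade 2, INR is not raised, and alkaline phosphatase is at most 8 x ULN. Then neither the permanent-stop criteria in 6.1.3.1 nor Table 11's combined-elevation row applies. Enhanced monitoring is being followed.

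| ALT or AST | Symptoms | Duration | Table 11 | Section 6.1.3.2 |
|---|---|---|---|---|
| 4 x ULN | none | 1 or 3 weeks | withhold | no criterion met |
| 6 x ULN | none | 1 week | withhold | no criterion met |
| 6 x ULN | none | 2 weeks | withhold | withhold |
| 9 x ULN | none | any | withhold | withhold |
| 4 x ULN | hepatitis symptoms | any | withhold | withhold |

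The rules therefore differ in two bands for asymptomatic, monitored subjects: above 3 and up to 5 x ULN at any duration, and above 5 and below 8 x ULN for under 2 weeks. Relative to Table 11's limit, the asymptomatic limits in 6.1.3.2 are 5/3 = 1.67 times as high (sustained 2 weeks) and 8/3 = 2.67 times as high (any time). A value of exactly 8 x ULN falls in neither of the upper bands of 6.1.3.2. The bilirubin (above 3 x ULN) and alkaline phosphatase (above 8 x ULN) limits agree in both places, so the mismatch is confined to ALT/AST.

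**3. Does any text set precedence?** Section 6.4 closes by naming Tables 9 and 11 as the nab-Sirolimus dose modification guidelines. Table 11 then sends the reader back to 6.1.3.1 and 6.1.3.2, so the question is not settled.

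**4. Scope of 6.1.3.2.** A subject without liver disease whose baseline AST or ALT is above 1 and up to 2.5 x ULN is eligible under criterion 5b. That subject fits neither population described in 6.1.3.2.

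**The case against.** **Pneumonitis.** The cell reads naturally as a general rule followed by grade-specific paragraphs. The restart is also tightly gated: the pneumonitis is noninfectious, it has recovered to Grade 1 or better within 3 weeks, the dose is reduced, there is evidence of benefit, and subjects who do not recover are withdrawn. Exclusion criterion 12 bars a history of pneumonitis or interstitial lung disease. All of this stands and makes the problem one of drafting. It does not supply the missing exception.

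A reader might apply the 3% Grade 3 rate in Section 1.2.1 to the 39 phase 2 subjects to count those affected. The documents do not support that. The rate is for oral rapamycin and rapalogs and covers all Grade 3 pneumonitis, while the two instructions diverge only for noninfectious cases that recover in time and show benefit. No rate is given for this combination and dose.

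**Liver.** A reader might infer that the two sections give opposite orders. They do not. Both only recommend withholding, 6.1.3.2 nowhere directs that dosing continue, and Section 6.1.2 permits a hold for any clinically significant AE. Every ALT/AST value above 3 x ULN that meets a 6.1.3.2 criterion also meets Table 11's, so an investigator who follows Table 11 breaches nothing.

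The gap between 5 and 8 x ULN is also narrow under current dosing. On the Day 1-only schedule, chemistry from Cycle 3 is drawn on Days 1 and 8. A rise found on Day 8 and still present at the next Day 1 (nominally Day 22) has lasted 22 - 8 = 14 days, so both rules withhold. What remains is mainly a rise first seen on Day 1, or on Day 15 of Cycles 1-2 (22 - 15 = 7 days). The gap above 3 and up to 5 x ULN is unaffected.

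**Scope.** A reader might infer that subjects outside the wording of 6.1.3.2 have no hold rule. They do: Table 11 has no baseline restriction and covers them.

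**Conclusion.** Two nab-Sirolimus safety rules are inconsistent as written and should be corrected. In Table 9, an unqualified permanent stop sits above a conditional restart for Grade 3 noninfectious pneumonitis. The restart is probably an intended exception that was not labelled. In the liver rules, Table 11 and the section it cites use different ALT/AST limits, with no statement of which prevails.

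The liver difference is limited to asymptomatic, monitored subjects in the two bands shown above. It rests on the event being graded 2 or higher and possibly related, and on bilirubin, INR and alkaline phosphatase staying below their own limits. No count of affected subjects is given for either rule, because the documents provide no usable rate. The correction concerns patient safety and consistent conduct, and it has no effect on the PFS endpoint or on power.

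**What to change.** 1. **Table 9.** Open the Grade 3 or higher respiratory cell with "Permanently discontinue ABI-009", followed by: except Grade 3 noninfectious pneumonitis with infection ruled out, as below. If a permanent stop is intended for all such events, delete the restart sentence.
2. **Table 11 and Section 6.1.3.2.** Use one ALT/AST threshold set in both places. The default should be a statement that the stricter Table 11 limit governs.
3. **Scope of 6.1.3.2.** Reword it to cover everyone admitted under criterion 5b, including subjects without liver disease whose baseline AST or ALT is up to 2.5 x ULN.

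The cost is amendment wording in Tables 9 and 11 and Section 6.1.3.2, with no change to sample size, endpoints or visits. The stricter liver rule has a small downside: more holds for asymptomatic rises. Choosing the looser set instead would mean that dosing may continue in the two bands where the rules now differ, which the sponsor should then state and justify.
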